8.1.9 Performing Adverse Events Assessments

The AE collection period for each subject starts with the signing of the ICF and completes when the subject ends the study. During the course of the study, the Investigator or designee shall routinely monitor each subject for the occurrence of any AE. Routine monitoring should include regular communication with the trial subject, review of laboratory results, assessment of anticoagulation, dialysis access, medication use, and review of the treatment details in the HemoCareTM cloud-based system as reported by the assigned HemoCareTM Hemodialysis System. Site team members should follow up and gather additional details from subjects when appropriate based on these information sources as well other data sources including but not limited to physical exams, vital signs, subject questionnaires, and concomitant medication listings.

In addition to AE solicitation, study sites should discuss the AE reporting process with their study subjects and encourage them to volunteer the applicable information to the appropriate site team members in real time. All site team members should likewise monitor and solicit information from subjects if an event is suspected based on subject conversations or data points collected. This level of open dialog should drive the AE collection and reporting process.

During the course of the study, controls will also be in place to consistently gather AE information during the Weekly Assessment. The site team members will use their clinical judgment to follow up with the subjects and report any applicable event(s).

The site investigator or designee will contact the subject weekly to discuss their current status, treatment, and condition. These timelines are minimum requirements

for the sites to follow, and sites should follow their local guidelines if more frequent communication is required (e.g., local standard of care or to follow up on current/recent events).

8.1.10 Adverse Event Reporting

8.1.10.1 Reporting Adverse Events to Sponsor/Designee

During the course of the study, the Investigator or designee will routinely monitor each subject for the occurrence of any AE/ADE. If an AE/ADE occurs, the Investigator or designee will complete the AE eCRF which includes the following:

- · Description of the event
- Start and stop date of the event
- Timing of the event (prior to first study treatment, during treatment setup, during treatment, within 4 hours after treatment ends, > 4 hours after treatment ends)
- Seriousness of the event (yes, no)
- Severity of the event (mild, moderate, or severe)
- Causality of the event (related to treatment and/or related to the IP)
- Action taken
- Outcome of the event (fatal, not recovered/not resolved, recovered/resolved with sequelae, recovered/resolved, and unknown)

All SAEs must be reported to the Sponsor/designee within 24 hours of the Investigator or designee becoming aware of its occurrence. The informed site team member should also contact their site monitor by phone or email to notify him/her of the event. This requirement is irrespective of whether the AE is thought to be possibly related to the study product or not.

[figure not shown]
8.1.11 Expedited Reporting of Serious Adverse Events and Suspected Unexpected Serious Adverse Reaction (SUSAR)

The Sponsor/designee will assess each SAE reported by the Investigator to determine if the SAE qualifies as an expedited report according to FDA criteria. Sponsor/designee will report to FDA according to the applicable time requirements.

Per regulations, when an Unexpected Adverse Device Effect (UADE) or SUSAR occurs Investigators will receive a letter from Sponsor/designee describing the UADE/SUSAR. The Investigator should file this letter within their Investigator Study Binder. Additionally, the expedited report letter should be submitted by the

Investigator to their IRB/REB, as appropriate per FDA regulations.

8.1.12 Device-Related Product Complaints

8.1.13 Trial Subject Reporting - Product Issues

Throughout the trial, HemoCare™ Hemodialysis System will record and report device alarms. The alarm time(s), code(s), and description(s) will be reported to the Sponsor as they occur.

This data will be maintained for end- of-study statistical analysis. Additionally, this data will be reviewed and trended by the Sponsor and/or designee for safety concerns or service requirements. In addition to device reported product issues, trial sites will also report product issues.

Trial subjects or care partners will be instructed to contact the on-call study site staff for any product issues which cannot be resolved using the User Guide or training tools. The

site staff will assist the subject in resolving the product issue using the device User Guide and training material. If the site is unable to resolve the product issue, site staff will be instructed to contact the Sponsor/designee for device support. The site staff will also contact the investigator or designee to discuss next steps for the trial subject in the event of an incomplete or missed treatment.

8.2 Clinical Laboratory Tests

8.2.1 Laboratory Parameters

A central laboratory will perform laboratory tests for hematology and serum chemistries.

Sites may order additional activated partial thromboplastin time (aPTT) testing as necessary at the discretion of the Investigator in order to maintain optimal heparin dosing.

Subjects will be in a seated or supine position during blood collection. Clinical laboratory tests are found in Table 2.

Table 2. List of Laboratory Tests

Serum Chemistry:

- Comprehensive metabolic panel (including glucose, calcium, sodium, potassium, total carbon dioxide or serum bicarbonate, chloride, urea, creatinine, ALP, ALT, AST, total bilirubin, serum albumin, and total protein) + serum phosphorus (pre-dialysis)
- Urea (pre and post-dialysis)
- Iron profile (pre-dialysis)

Hematology:

CBC (pre-dialysis)

Coagulation:

 Activated partial thromboplastin time (aPTT)

CBC=complete blood count; ALP=alkaline phosphatase; ALT=alanine amino transferase; AST=aspartate amino transferase; aPTT=activated partial thromboplastin time

Laboratory evaluations will be performed as outlined in Appendix 2.

The Investigator will receive the laboratory results for review and signature. The Investigator will be notified of any laboratory value that is outside of the normal range, as defined by the central laboratory and included as part of the laboratory manual. If a clinically meaningful change from baseline or the previous visit occurs for any laboratory value and results in medical intervention, as judged by the Investigator, the laboratory abnormality will be recorded as an AE on the eCRF.

Baseline observation data for all assessments are defined in section 11.4 and unless otherwise specified therein, are the last observational values brought forward from DEKA Protocol DKPL-00057-001, Sample Collection, Storage and Shipping.

A study specific Laboratory Manual will be provided by the central laboratory to the Investigators and will include detailed instructions on the collection, preparation, storage, and shipping procedures for blood samples and the appropriate laboratory ranges. If a local laboratory is used for aPTT testing, the local laboratory will be required to provide kits and instructions to Investigators.

9 STUDY SCHEDULE AND PROCEDURES

9.1 Schedule of Evaluations and Procedures

All clinical study evaluations will be performed according to Appendix 1, Schedule of Evaluations and Procedures and the instructions listed below. If a subject discontinues from the study prematurely, every attempt will be made to perform all of the procedures and evaluations that are scheduled for the final visit (i.e., End of Study visit).

9.2 Qualification Visit

The Qualification visit will be conducted after completion of DEKA Protocol DKPL-00057-001. The study must be explained to the subjects and care partners at this visit or prior, and all subjects and care partners must sign an ICF before any study-related procedures are performed. The following procedures will be performed and, as appropriate, recorded on the eCRF at the Qualification visit:

- Obtain informed consent of the subject and care partner.
- · Update medical history including resolved AEs.
- Update concomitant medications.
- Update AEs including ongoing AEs.

9.3 Treatment Period

This period begins immediately following enrollment and will last until subject is discontinued from the study or Market Authorization for the HemoCareTM Hemodialysis System is granted. The following information will be collected, and procedures or evaluations will be performed:

- Treatment with the HemoCare™ Hemodialysis System as prescribed by the Investigator or designee.
- Clinical laboratory evaluations as specified in Appendix 2.
- Care partner will be present for all treatments.
- At each treatment:
 - Clinical observations

- Adverse events/serious adverse events/adverse device effects
- Concomitant medications
- Treatment data from HemoCare™ Treatment Device
- Device-related product issues (Device-related product complaints)
- Chloramine, and if applicable, pH and conductivity testing
- Ultrapure sampling will be done quarterly or per site policy or local regulations.
- The investigator or designee will assess each subject on a weekly basis according
 to standard-of-care and/or site regulations. The assessment may include blood
 pressure, fluid status and dialysis prescription.

9.4 End of Study Visit or Early Termination Procedures

The following information will be collected, and procedures or evaluations will be performed at the final visit:

- · Physical exam including weight
- Vital signs
- 12-lead ECG
- Adverse events/serious adverse event/adverse device effect
- Concomitant medications
- Clinical laboratory evaluations as specified in Appendix 2
- Device-related product issues (device-related product complaints)
- Device related AEs and SAEs will be followed post-study until resolution or stabilization

If a subject discontinues from the study, every attempt should be made to perform all of the procedures and evaluations that are scheduled for the final visit (i.e., End of Study visit). Upon exiting the study, subjects who discontinued early will be transitioned as prescribed by their physician. The HemoCare Hemodialysis System used for these subjects will be removed from their home by the designee of the study sponsor.

10 DATA MANAGEMENT, QUALITY CONTROL AND QUALITY ASSURANCE

10.1 Clinical Database

The designated CRO will be responsible for activities associated with the data management of this study. This will include setting up a relevant database and data transfer mechanisms, along with appropriate validation of data and resolution of queries. Data generated within this clinical study will be handled according to the relevant standard operating procedures (SOPs) of the data management and biostatistics departments of sponsor or the designated CRO.

Study centers will enter data directly into an EDC system by completing the CRF via a secure internet connection. Data entered into the eCRF must be verifiable against source documents at the study center. Data to be recorded directly on the eCRF will be identified and the eCRF will be considered the source document. Any changes to the data entered into the EDC system will be recorded in the audit trail and will be FDA CFR 21 Part 11 compliant.

Medical coding will use Medical Dictionary for Regulatory Activities (MedDRA) for concomitant diseases and AEs and WHODrug for medications.

Missing or inconsistent data will be queried in writing to the Investigator for clarification. Subsequent modifications to the database will be documented.

10.2 Audits and Inspections

In addition to the routine monitoring procedures and in accordance with GCP principles, GCP audits might well be performed by the Quality Assurance members of Sponsor/Designee.

These audits of clinical research activities are in accordance with applicable regulatory requirements, Sponsor/designee internal policies and procedures, to evaluate compliance with the principles of GCP. A Regulatory Authority may also wish to conduct an inspection (during the study or even after its completion). If a Regulatory Authority requests an

inspection, the Investigator must immediately inform the Study Monitor of Sponsor/designee that this request has been made.

11 STATISTICAL CONSIDERATIONS

11.1 General Considerations

Further details of the planned statistical methods presented below will be provided in the study statistical analysis plan (SAP). The purpose of the SAP is to further elaborate the statistical methods described in the protocol and describe analysis conventions to guide the statistical programming work.

Unless otherwise noted, all analyses will be performed using Statistical Analysis Software (SAS®), SAS/GRAPH® and SAS/STAT® software, Version 9.4 of SAS for Windows, copyright® 2002-2008 SAS Institute Inc., on a Microsoft Windows Server. Statistical Analysis Software and all other SAS Institute Inc. product or service names are registered trademarks or trademarks of SAS Institute Inc., Cary, NC, USA). ¹⁹

11.2 Determination of Sample Size

Plan to enroll all subjects who complete the DEKA Protocol DKPL-00057-001. The sample size is not based on a statistical power calculation.

11.3 Analysis Populations

The Intent-to-Treat (ITT) population will include all subjects who have used the HemoCare™ Hemodialysis System at least once in this rollover study. All analyses will be performed on the ITT population unless otherwise noted.

11.4 Demographics and Baseline Characteristics

Demographic data include age, gender, race, body mass index (calculated as weight/height×height [kg/m²]), and ethnicity.

Baseline observation data for all assessments are defined herein and unless otherwise specified, are the last observational values brought forward from DEKA Protocol DKPL-00057-001.

Other baseline data include:

- General medical history; medical condition or surgery items collected on the eCRF will be coded to the appropriate System Organ Class (SOC) and Preferred Term (PT) using the Medical Dictionary for Regulatory Activities (MedDRA), Version 17.1 or higher.
- 2. Renal medical history,

- a. type of first chronic dialysis treatment (HD or PD)
- b. primary renal disease etiology
- elapsed time since first chronic dialysis treatment of HD or PD and by modality (years)
- 3. Vital signs including height (cm), weight (kg), blood pressures (mmHg), pulse rate (beat/minute), temperature (degrees C), and respiratory rate (breaths/minute)
- Hemodialysis prescription parameters from End of Study visit of DEKA Protocol DKPL-00057-001.
 - a. duration of treatment session (hours)
 - b. calculated total treatment time per week across all sessions (hours)
 - c. blood flow rate (mL/minute)
 - d. dialysate flow rate (mL/minute)
 - e. dialysate volume (L)
 - f. heparin loading dose (units)
 - g. total heparin infusion (units)
 - h. target dry weight (kg)
 - i. total fluid removed (L) and weight loss (kg)
- 5. Type and location of dialysis access
- Laboratory parameters from End of Study visit of DEKA Protocol DKPL-00057-001.
 - a. CBC
 - b. Comprehensive metabolic panel plus serum phosphorus
 - c. Iron profile

Continuous variables will be summarized by sample size (N), mean, standard deviation, minimum, and maximum. Frequency and percentages will be provided for the categorical variables.

11.5 Primary Endpoints

11.5.1 Primary Safety Endpoint(s)

Safety endpoints will summarize the number of subjects having AE and the number of AE: Number and proportion of subjects having AE and SAE, Number of AE and SAE, and rate of AE/100-Treatment and SAE/100-Treatment.

All the above indicator will be broken down by SOC, PT, Anticipated/unanticipated, and Related/un-related.

Safety will be assessed by evaluating AEs. In addition, monthly laboratory draws will be assessed.

Adverse events will be mapped to a primary MedDRA SOC and PT. Anticipated AEs and SAEs (includes all AEs related to dialysis as identified in Section 8.1.7) and unanticipated AEs and SAEs (excludes all AEs related to dialysis identified in Section 8.1.7) will be summarized during by SOC and PT. In addition, all device-related AEs and SAEs will be summarized by SOC and PT.

An overview of the total number of AEs and SAEs (anticipated, unanticipated, and device- related) will be provided. In addition, an overview will be provided of the total number of subjects having at least one:

[figure not shown]
- a. anticipated AE
- b. anticipated SAE
- c. unanticipated AE
- d. unanticipated SAE
- e. device-related AE
- f. device-related SAE (UADE)

The proportion of subjects having at least one AE within each of these six AE subgroups will be summarized descriptively.

Furthermore, the proportion of subjects having AEs within each of these six AE subgroups will be summarized by SOC, PT and severity (mild, moderate or severe) for the most severe rating of each AE per subject. And, the AE rate per 100 HemoCareTM Hemodialysis System treatments will be calculated.

Descriptive summary statistics will be provided for the visit values and change from DEKA Protocol DKPL-00057-001 baseline in monthly laboratory draws.

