8 ADVERSE EVENT REPORTING

8.1 Adverse Events and Serious Adverse Events

An AE is any untoward medical occurrence in a subject administered a study product and which does not necessarily have a causal relationship with the treatment or study product.

An AE can therefore be any unfavorable and unintended sign (including an abnormal laboratory function), symptom (e.g., rash, pain, discomfort, fever, dizziness, etc.), disease (e.g., bacteremia, pancreatitis, etc.) or outcome of death temporally associated with the use of the study product, whether or not the event is considered to have a causal relationship with the study product.

Laboratory and vital sign abnormalities qualify as AEs if medical intervention is required to treat or address the abnormality, if the subject must be discontinued from the study due to the abnormality, or if the value exceeds specific limits defined by the protocol as qualifying it as an AE (see Appendix 4).

An elective procedure/surgery that occurs during the course of a study but is being performed for a documented pre-existing condition and was pre-planned prior to study entry will not qualify as an AE. If, however, the pre-existing condition unexpectedly deteriorates during the study requiring the procedure/surgery to be performed earlier than planned, the condition for which the procedure/surgery is being performed will qualify as an AE.

Adverse events will be collected starting from the time the subject signs the ICF until the end of the study. If an AE occurs, a full description of the event should be recorded including the date of onset, severity, time course, description, actions taken, and causal relationship of the AE to the study product(s). Investigators should review and reference the Causality definitions below when determining relationship of the AE to the study product. The Investigators may also discuss the event(s) with the Medical Monitor, but the Investigator must make, document and report the relationship for every AE. All AEs must be documented in source documents and on the eCRFs, no matter how common they are for a particular subject and regardless of the causality assigned by the Investigator.

All AEs and SAEs, regardless of relatedness, should be actively solicited and recorded.

Additionally, any AE voluntarily reported by the subject should be recorded and verified by the Investigator or designee on the appropriate source documents and eCRF pages.

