8.1.7 Adverse Events Related to Hemodialysis Therapy (Anticipated Adverse Events)

The following are common adverse reactions (signs, symptoms and diagnoses) that have been reported related to HD therapy: hypotension; hypertension; muscle cramps; nausea; vomiting; headache; chest pain; back pain; itching; fever; chills; disequilibrium syndrome; hypersensitivity (allergic) reactions including asthmatic reactions, respiratory arrest, pruritus, urticaria, erythema, and peripheral and facial edema; hypovolemia; hypervolemia; cardiac arrhythmia; cardiac tamponade; intracranial bleeding; seizures; hemolysis; air embolism including micro-air embolism; blood loss; infection; access-related problems including infiltration;

abdominal pain; fluid overload; hematuria; bleeding; and electrolyte imbalance.¹⁵⁻¹⁸ Definitions of these adverse reactions are provided in Appendix 4.

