Abdominal pain: Pain occurring in the portion of the trunk of the body lying between the thorax and the pelvis. The pain can be any unpleasant sensory and emotional experience arising from actual or potential tissue damage or described in only the perception of an uncomfortable stimulus but also the response to that perception.

Fluid Overload: Excess intravascular, interstitial and/or intracellular body fluids. This may manifest with swelling of the extremities, engorged neck vein and rales.

Hematuria: Blood in the urine.

Bleeding: Emitting blood, as from an injured vessel, body orifice, or mucosa.

Electrolyte imbalance involves the following based on serum levels. The definitions are from the CHL.

Hyponatremia: Sodium levels <130 mEq/L Hypernatremia: Sodium levels >146 mEq/L Hypokalemia: Potassium levels <3.0 mEq/L Hyperkalemia: Potassium levels >5.6 mEq/L

Hypocalcemia: Calcium levels < 8.0

mg/dLHypercalcemia: Calcium levels >10.5 mg/dLMetabolic alkalosis: Bicarbonate level >29 mEq/L Metabolic acidosis: Bicarbonate level <20

mEq/L

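### Section 11.5.1 plans no count of subjects below or above the two-sided laboratory limits, and the adverse event tables fill that gap only in part

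*Combined protocol and SAP*

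**What the plan says.** Monthly laboratory draws are part of the safety endpoint in the synopsis and in Section 11.5.1. Their planned analysis is one sentence, which opens "Descriptive summary statistics will be provided for the visit values and change from"; the reference for change is the feeder-study baseline. Section 11.5.1 does not say which statistics are meant. The only list is in Section 11.4, which covers baseline characteristics: "Continuous variables will be summarized by sample size (N), mean, standard deviation, minimum, and maximum".

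Appendix 4 gives numeric limits under the line "Electrolyte imbalance involves the following based on serum levels". For sodium and potassium they read "Hyponatremia: Sodium levels <130 mEq/L Hypernatremia: Sodium levels >146 mEq/L Hypokalemia: Potassium levels <3.0 mEq/L Hyperkalemia: Potassium levels >5.6 mEq/L". Calcium (below 8.0 or above 10.5 mg/dL) and bicarbonate (below 20 or above 29 mEq/L) follow in the same form.

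Two sections say when a laboratory value becomes an adverse event (AE):

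- Section 8.1 lists three alternative routes: medical intervention, discontinuation, or "if the value exceeds specific limits defined by the protocol as qualifying it as an AE (see Appendix 4").
- Section 8.2.1 describes recording under this condition: "If a clinically meaningful change from baseline or the previous visit occurs for any laboratory value and results in medical intervention". The judgment is left to the site, and the abnormality then goes on the eCRF as an AE.

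Electrolyte imbalance closes the list of anticipated events in Section 8.1.7 ("abdominal pain; fluid overload; hematuria; bleeding; and electrolyte imbalance"). Section 11.5.1 counts subjects with AEs by SOC and PT. Appendix 3 sets a pre-dialysis phosphorus target of 2.7 to 5.5 mg/dL; Appendix 4 has no phosphorus entry.

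**The concern.** For an analyte that can be harmful in either direction, the safety questions are how many subjects were too low, how many were too high, and whether they were already so at entry. A mean, or a mean change, answers none of these, because subjects moving up and subjects moving down offset each other. SD, minimum and maximum help, but they give neither a number of subjects nor a persistence.

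Opposite movements are plausible here. Section 6.3 lets subjects alter frequency, duration and blood flow from treatment to treatment within an approved range. At stake is whether the laboratory half of the safety endpoint can report the share of subjects outside the protocol's own limits from measured values, or whether that share must be inferred from AE entries whose recording rule is stated in two ways.

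**Working it through.** The plan has no figure to reproduce: Section 11.2 states that the sample size is not based on a power calculation. The check has four parts.

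**1. Are the limits two-sided?** Appendix 4 lists four analytes (sodium, potassium, calcium, bicarbonate), each with a low and a high term: 4 × 2 = 8 of 8 terms. All of them are two-sided.

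**2. Can the mean stay fixed while values leave the limits?** Assume normal values. The proportion of draws outside limits L and U is Φ((L − μ)/σ) + 1 − Φ((U − μ)/σ). The limits come from Appendix 4; every μ and σ is an assumption.

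| Analyte (limits) | Assumed mean | Assumed SD | Below + above | Outside, per draw |
|---|---|---|---|---|
| Potassium (3.0, 5.6) | 4.5 | 0.6 | 0.0062 + 0.0334 | 4.0% |
| Potassium (3.0, 5.6) | 4.5 | 0.9 | 0.0478 + 0.1108 | 15.9% |
| Bicarbonate (20, 29) | 24.5 | 2.0 | equal halves | 2.4% |
| Bicarbonate (20, 29) | 24.5 | 3.0 | equal halves | 13.4% |

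With potassium centred instead at the midpoint, (3.0 + 5.6)/2 = 4.3, SDs of 0.5, 0.7 and 1.0 give 0.9%, 6.3% and 19.4%. The mean change is zero throughout.

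**3. Do SD, minimum and maximum supply the count?** Assume 30 subjects, which is about the number the feeder study aims to bring into its Unassisted Home Evaluable Period (Section 2.1). Put k subjects at potassium 2.7, k at 5.9, and space the remaining 30 − 2k evenly from 3.7 to 4.9.

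| k on each side | Mean | SD | Min / max | Outside (2k of 30) |
|---|---|---|---|---|
| 0 | 4.30 | 0.36 | 3.70 / 4.90 | 0 |
| 1 | 4.30 | 0.55 | 2.70 / 5.90 | 2 |
| 3 | 4.30 | 0.80 | 2.70 / 5.90 | 6 |
| 5 | 4.30 | 0.99 | 2.70 / 5.90 | 10 |

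Minimum and maximum show that both limits were crossed, but they are identical for 2, 6 and 10 subjects. The SD moves but does not fix the count. At mean 4.30 and SD 0.80 this data set has 6/30 = 20% outside, whereas a normal distribution with mean 4.3 and SD 0.8 has 10.4%.

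**4. Does the AE route supply the count?**

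- *Sodium, potassium, calcium, bicarbonate.* Under Section 8.1 a value beyond an Appendix 4 limit is an AE whether or not it is treated. It is then counted by PT, with low and high separated where the PTs differ. Under Section 8.2.1 the recording described is for changes that lead to intervention. An untreated excursion is an AE by the first text and is not mentioned by the second.
- *Alerts.* Section 8.2.1 notifies the Investigator of values outside the central laboratory's normal range, not of values beyond the Appendix 4 limits.
- *New or pre-existing.* Appendix 1 carries ongoing AEs over from the feeder study. Section 11.5.1 names no split between carried-over and new events.
- *Denominator.* AE rates are per 100 treatments, while Appendix 2 schedules these draws monthly. No planned figure gives the proportion of subject-months outside a limit.
- *Phosphorus.* With no Appendix 4 limit, a value outside 2.7 to 5.5 mg/dL becomes an AE only through intervention or discontinuation. Otherwise it need not be counted anywhere.

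**The case against.** The strongest reply is that the AE tables already do this work. Section 8.1 turns a breach of an Appendix 4 limit into an AE and requires every AE to be documented, however common it is for the subject. Section 8.1.9 makes laboratory review part of AE monitoring, and under Section 8.2.1 the Investigator receives and signs the results. Section 8.2.1 is also not worded as the only route. A reader might infer from Section 11.5.1 that subjects outside the limits go uncounted; the documents do not support that. What survives is narrower: they are not counted from the laboratory data, and the AE count depends on which recording text a site follows.

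A reader might likewise infer that only means are planned. That is wrong too, since Section 11.4 lists SD, minimum and maximum, although for baseline data.

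Two further replies carry weight. Section 11.1 defers detail to a separate SAP that is not in the text available, and no Section 11.6 is visible between 11.5.1 and 11.7, so a shift table may be planned elsewhere. And this is a small, descriptive continued-access study in which no hypothesis or decision rule rests on the laboratory means. Both limit the weight of the point. Neither supplies the missing display in the section that defines the endpoint, and neither covers phosphorus.

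**Conclusion.** The point holds in a limited form. As written, the laboratory analysis gives no number of subjects below or above each limit, no direction and no persistence. The AE tables replace that count only if Section 8.1 governs, and they do not cover untreated phosphorus values that do not lead to discontinuation. Sections 8.1 and 8.2.1 must be reconciled; which rule should apply is not a statistical question and is left open here.

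A reader might take the illustrations to mean that the report would show no change while the share of affected subjects rises several-fold. The documents do not support that. The rise from 4.0% to 15.9% comes entirely from an SD widening of one half (0.9/0.6 = 1.5), and that SD would stand beside the mean if the Section 11.4 list is used. The percentages are per monthly draw, not per subject. The means, SDs, normal shape and group of 30 are all assumed, and nothing in the documents predicts such a widening. They show what the planned statistics cannot distinguish and are not estimates for this trial. The change is a cheap improvement and does not correct a result that would otherwise be wrong.

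**What to change.** In Section 11.5.1, and in the SAP it points to, keep the existing tables and state that their statistics are those listed in Section 11.4. Add the following, computed from central laboratory values for sodium, potassium, calcium and bicarbonate against the Appendix 4 limits, and for phosphorus against the protocol's own Appendix 3 range (for display only):

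1. the number and percentage of subjects with any monthly value below the lower limit and, separately, above the upper limit;
2. the proportion of subject-months outside each limit;
3. a shift table (below, within, above) from the Section 11.4 baseline to the worst post-baseline value in each direction.

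Separately, reconcile the AE recording texts in Sections 8.1 and 8.2.1, so that readers know what the AE counts of electrolyte imbalance contain.

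The cost is some SAP wording and a few programmed tables from data already collected. The downside is more descriptive output, with pre-existing abnormalities to be read from the baseline side of the shift table. No clinical limit or management rule changes.
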